11.5 Other Safety Variables

Anti-PTH antibodies will be assessed at Day 1 (pre-dose) and at Follow-up. The results at each timepoint will be summarized by ethnic group, and these data will be listed.

12. CLINICAL PHARMACOKINETIC AND PHARMACODYNAMIC ANALYSES

12.1 Pharmacokinetics Population and Pharmacodynamic Population

The Pharmacokinetic Set consists of all subjects who have received at least 1 dose of investigational product and have at least 1 evaluable post dose PK concentration value.

The Pharmacodynamic Set consists of all subjects who have received at least 1 dose of investigational product and have at least 1 evaluable post dose PD concentration value.

12.2 Handling BLQ, Zero Values, Missing Values

The following procedures will be used for original plasma PTH concentrations and serum PD data below the lower limit of quantification (LLOQ) and baseline-adjusted PTH and PD concentration data:

- Samples that are BLQ are reported as <LLOQ on the data listings, where LLOQ is replaced by the actual value for LLOQ for specific PK or PD assay.
- Samples that are BLQ are treated as zero in the calculation of summary statistics (e.g. mean, SD, etc.) for the plasma concentrations at individual time points.
- Mean concentrations are reported as zero if all values are BLQ or zero, and no other descriptive statistics are reported. If the calculated mean (\pm SD) concentration is less than the LLOQ, the value will be reported as calculated. The mean values derived using these conventions will be used to create the mean plasma concentration versus time plots.
- For calculation of area under the plasma concentration curve (AUC), BLQ values are set equal to zero in the dataset loaded into WinNonlin for pharmacokinetic analysis. WinNonlin uses the zero values that occur before the first time point with a concentration greater than LLOQ. Values that are BQL after the first measurable concentration are set to “missing” in the dataset loaded into WinNonlin.
- Missing values will not be imputed.

12.3 Pharmacokinetic Methods

All summaries and analyses of the pharmacokinetic data will be based on the Pharmacokinetic Set. After database lock, a visual inspection of concentration-time profiles and pharmacokinetic parameters will be performed by PRA to determine dataset integrity and potential outliers. Descriptive statistics of pharmacokinetic parameters may be calculated with and without subjects with potential outlier data. Subjects with potential outlier data will be reviewed by Shire for inclusion/exclusion from the descriptive statistics on a case-by-case basis.

12.3.1 Original PTH Concentration Data

For non-Hispanic, Caucasian subjects on Day 1 and for subjects of Japanese descent on Day 1, 4 and 7, samples for pharmacokinetic analysis are taken at Predose 1 (within 90 ± 30 min prior to dose administration), Predose 2 (within 30 min prior to dose administration), and 10, 20, 30 and 45 minutes, 1, 1.25, 1.5, 2, 2.5, 3, 4, 6, 8, 12, 16, 24 hours after administration of the investigational product. Plasma concentrations of PTH will be measured using a validated analytical method.

Individual original PTH concentrations will be listed and summarized with descriptive statistics by ethnic group, dose and time point, including number, arithmetic mean, standard deviation, coefficient of variation [CV%], median, minimum, and maximum. Figures of individual original concentration-time profiles and mean (\pm SD) by ethnic group and dose will be generated on linear and semi-log scale. The mean plot will be created by overlaying each ethnic group and dose on the same figure.

12.3.2 Baseline-adjusted PTH Concentration Data

Baseline-adjusted PTH concentrations are to be calculated by subtracting baseline endogenous PTH from the original PTH concentrations. Such baseline adjustment is subject- and dose-specific. For each subject, baseline is defined for each dosing period as follows: the baseline for Day 1 dosing is defined as the average predose concentration on Day 1 (average of predose 1 and predose 2 PTH concentrations); for subjects of Japanese descent the baseline for Day 4 dosing is defined as the average predose concentration on Day 4 (average of predose 1 and predose 2 PTH concentrations); the baseline for Day 7 dosing is defined as the average predose concentration on Day 7 (average of predose 1 and predose 2 PTH concentrations). If the baseline-adjusted PTH concentration gives a negative value, then the baseline-adjusted PTH concentration should be set to zero. In the terminal log-linear phase, if two consecutive baseline-adjusted PTH concentrations give negative values, then all the subsequent values will be set to zero.

Individual baseline-adjusted PTH concentrations will be listed and summarized by ethnic group and dose as in section 12.3.1. Individual plots and mean plots will be generated in the same way as described in section 12.3.1 but using the baseline-adjusted PTH concentrations. If the baseline-adjusted PTH concentration is zero, it will be presented as missing on the semi-log scale.

12.3.3 Pharmacokinetic Parameters

The pharmacokinetic analysis will be conducted by using WinNonlin Phoenix version 6.3 or higher (Pharsight Corporation, Mountain View, California, USA). Pharmacokinetic parameters will be determined from the plasma PTH concentration-time data by non-compartmental analysis. Both original and baseline-adjusted PTH concentrations will be used to compute all the PK parameters respectively.

The pharmacokinetic parameters will include, but may not be limited to:

- C_{max} : Maximum observed concentration, to be reported in the unit of pg/mL (both original and baseline-adjusted PTH)
- t_{max} : Time of maximum observed concentration sampled during a dosing interval, to be reported in the unit of hour (both original and baseline-adjusted PTH)
- AUC_{last} : Area under the curve from the time of dosing to the last measurable concentration. Calculated using the linear up/log down method, to be reported in the unit of pg.hr/mL (both original and baseline-adjusted PTH)
- AUC_{0-inf} : Area under the curve extrapolated to infinity calculated as $AUC_{last} + C_{last}/\lambda_z$. Calculated using the linear up/log down method, to be reported in the unit of pg.hr/mL (for baseline-adjusted PTH only)
- %AUC extrapolated: % of AUC extrapolated from the last measurable concentration to infinity over $AUC(0-inf)$ (for baseline-adjusted PTH only)
- λ_z : Elimination rate constant associated with the terminal (log-linear) portion of the curve. The log-linear portion of the curve must contain at least three points after T_{max} and have an r^2 value ≥ 0.8 (for baseline-adjusted PTH only)
- $t_{1/2}$: Terminal half-life, calculated as $0.693/\lambda_z$ (for baseline-adjusted PTH only)
- CL/F: Apparent total body clearance, calculated as Dose/ AUC_{0-inf} (for baseline-adjusted PTH only)
- Vd_z/F : Apparent volume of distribution, calculated as Dose/ $AUC_{0-inf} * \lambda_z$ (for baseline-adjusted PTH only)

All PK parameter calculations will be performed using actual sampling times calculated relative to the day of rhPTH(1-84) administration. The PK parameters λ_z , $t_{1/2}$, AUC_{0-inf} , CL/F, and Vd_z/F will not be calculated for subjects with PTH concentration-time profiles (baseline-adjusted) that do not exhibit a terminal log-linear phase, or if %AUC extrapolated $> 20\%$.

In addition, body-weight adjusted AUC_{last} (calculated as $AUC_{last}/\text{body-weight}$), AUC_{0-inf} (calculated as $AUC_{0-inf}/\text{body-weight}$), C_{max} (calculated as $C_{max}/\text{body-weight}$), CL/F (calculated as $CL/F/\text{body-weight}$), and Vd_z/F (calculated as $Vd_z/F/\text{body-weight}$) will be calculated based on baseline-adjusted PTH concentrations.

In addition, dose-normalized AUC_{last} (calculated as AUC_{last}/Dose), AUC_{0-inf} (calculated as AUC_{0-inf}/Dose), and dose-normalized C_{max} (calculated as C_{max}/Dose) will be calculated based on baseline-adjusted PTH PK parameters.

Baseline-adjusted PK parameters will be the primary PK endpoints, and other PK parameters will be the secondary PK endpoints.

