3.2 Rationale for Dose Selection and Study Design Elements

The primary objective of this study is to compare the PK profile of plasma rhPTH(1-84) between subjects of Japanese descent and non-Hispanic, Caucasian volunteers. Although endogenous PTH levels are different between healthy subjects and patients with hypoparathyroidism, historically, evaluations of different formulations, injection devices and dose proportionality, with PK as the primary objective, have been conducted in healthy subjects due to the distinct PK profile of plasma rhPTH(1-84) following subcutaneous administration compared to endogenous PTH. The PK profile of rhPTH(1-84) following subcutaneous administration had been shown to be similar between healthy subjects and patients with hypoparathyroidism in previous studies. Therefore, this study is to be conducted in healthy subjects. Due to the presence of endogenous PTH in healthy subjects and that the current PTH assay measures the total PTH concentration (combination of both endogenous PTH and rhPTH [the assay cannot distinguish between endogenous PTH and administered rhPTH(1-84)]), the PK analysis will be performed based on both the original and baseline-adjusted PTH concentrations. Due to the potential differences in body weight between enrolled subjects of Japanese descent and non-Hispanic, Caucasian subjects, in addition to the non-body weight adjusted PK parameters we will also use body weight-adjusted PK parameters for comparison.

rhPTH(1-84) (Natpara), is currently approved in the US at doses of 25, 50, 75, and 100 μ g administered once daily. rhPTH(1-84) has demonstrated dose-proportional PKs over this dose range in studies performed in the western countries. No significant differences in either the PKs or PDs of rhPTH(1-84) are anticipated between Japanese and non-Japanese; therefore, the 100 μ g dose, the highest marketed dose, will be used in this study for direct comparative purposes. Further doses of 25 μ g and 50 μ g will be used in the subjects of Japanese descent to examine the dose proportionality of PKs in Japanese subjects

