9.8 Pharmacokinetic and Pharmacodynamic Analyses

9.8.1 Pharmacokinetic Analysis

All the PK analyses will be performed using the PK set.

A PK evaluation of PTH concentrations and baseline-adjusted PTH concentrations will be performed following the administration of rhPTH(1-84) administered on Day 1 for non-Hispanic, Caucasian subjects and Days 1, 4 and 7 for subjects of Japanese descent.

Pharmacokinetic parameters will be calculated from original and baseline-adjusted plasma concentration-time data using noncompartmental methods and all calculations will be based on actual sampling times. Baseline is defined as the average Day 1 predose concentration for all subjects (and the Day 4 and Day 7 average predose concentration for the subjects of Japanese descent for those respective dosing intervals). Pharmacokinetic parameters will be estimated based on noncompartmental analysis and will include, but not be limited to, the following:

- C_{max} : Maximum concentration occurring at t_{max}
- t_{max} : Time of maximum observed concentration sampled during a dosing interval
- AUC_{last} : Area under the curve from the time of dosing to the last measurable concentration
- λ_z : First order rate constant associated with the terminal (log linear) portion of the curve
- $t_{1/2}$: Terminal half-life
- CL/F : Apparent clearance
- $Vd_{z/F}$: Apparent volume of distribution

Non-body weight adjusted and body weight-adjusted AUC_{last} , C_{max} , CL/F , and Vd_z/F will be estimated. In addition, dose-normalized baseline adjusted AUC_{last} and C_{max} will be calculated.

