- On Day 1, all study subjects will receive rhPTH(1-84) as a single 100 μ g SC injection in the mid-thigh.
- On Day 4, and Day 7, all subjects of Japanese descent will receive rhPTH(1-84) as a single SC injection in the mid-thigh of either 25 μ g or 50 μ g depending upon randomization assignment. Administration of rhPTH(1-84) in subjects of Japanese descent in the mid-thigh should be randomized locally so that an equal number of subjects receive the first dose in the right thigh and an equal number in the left thigh. Subsequent doses should be administered in the opposing thigh to the last dose.

Assessments

[figure not shown]
- Serial blood samples for PK analysis will be collected on Day 1 (and Day 4 and Day 7 for the subjects of Japanese descent) for the determination of parathyroid hormone (PTH) concentrations at pre-dose and up to 24 hours post dose. These blood samples will be collected according to the Schedule of Assessments.
- Serial blood samples for PD analysis will be collected on Day 1 (and Day 4 and Day 7 for the subjects of Japanese descent) at pre-dose and up to 24 hours post dose for the determination of serum calcium, phosphate, and albumin concentrations.
- Safety and tolerability will be determined through assessment of treatment-emergent adverse events (TEAEs) from Day 1 time of dose up to the follow-up visit and vital signs, electrocardiogram (ECG) findings, and clinical laboratory evaluations on Day 1 pre-dose and up to 24 hours post dose for the non-Hispanic, Caucasian subjects and Day 1 pre-dose and up to 24 hours post last dose (Day 8) for the subjects of Japanese descent.
- Additional blood samples for safety purposes will be collected for assessment of anti-PTH antibodies.

Follow-up

- A post treatment follow-up visit will be completed 30 (± 2) days after the last dose of investigational product for each subject.

Figure 1 Study Design Flow Chart

This study is an open-label study to evaluate the PK and PD profiles, safety, and tolerability of single doses of rhPTH(1-84) in healthy adult subjects of Japanese descent (Group B) and matched healthy, adult non-Hispanic, Caucasian subjects (Group A). Group A and Group B need not be dosed at the same time.

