2.5 Determination of Sample Size

No formal calculations were performed to determine sample size for this study. The sample size is based on feasibility and is similar to that of comparable studies.

A total of 24 subjects will be enrolled: 12 non-Hispanic, Caucasian subjects and 12 subjects of Japanese descent (1:1 male: female). Non-Hispanic, Caucasian subjects will be matched to Japanese subjects based on sex, age (± 7 years), and body mass index ($\pm 15\%$).

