2.6 Multiplicity Adjustments for Type I Error Control

Not applicable, as the statistical analyses are for exploratory rather than confirmatory purposes.

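### SAP 12.3.3 divides AUC and Cmax by body weight at a fixed dose, which runs opposite to its own CL/F per kg and can distort the weight-adjusted ethnic comparison (descriptive outputs only)

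*SAP*

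**What the plan says.** Protocol 3.2 gives the reason for weight adjustment: "Due to the potential differences in body weight between enrolled subjects of Japanese descent and non-Hispanic, Caucasian subjects". It goes on to say that, besides the unadjusted parameters, "we will also use body weight-adjusted PK parameters for comparison". Protocol 9.8.1 lists "Non-body weight adjusted and body weight-adjusted" AUClast, Cmax, CL/F and Vdz/F but gives no formula, so the SAP definition is the only one.

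SAP 12.3.3 supplies it: "In addition, body-weight adjusted AUC_{last} (calculated as $AUC_{last" over body weight, and the same division for AUC0-inf, Cmax, CL/F and Vdz/F. The same section defines CL/F as "Apparent total body clearance, calculated as Dose" over AUC0-inf.

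The dose is not scaled to weight. SAP 2.1 states "On Day 1, all study subjects will receive rhPTH(1-84) as a single" 100 µg injection. Under SAP 2.5, Caucasian subjects are "matched to Japanese subjects based on sex, age" (±7 years) and BMI (±15%). Weight is not a matching factor.

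The weight-adjusted parameters go to Table 2.1.5, to Listing 5.5 and, for Cmax, AUClast and AUC0-inf at 100 µg, to the side-by-side box plots of Figure 2.1.11 (SAP 12.3.4.1). None is among the parameters for the Welch comparisons or forest plots in SAP 12.3.4.2.

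**The concern.** At a fixed dose a lighter subject receives more drug per kg. A weight adjustment of exposure should allow for that, by relating exposure to dose per kg. Dividing AUC or Cmax by weight does the opposite, and raises the value further in the lighter subject. Clearance is the reciprocal of exposure at a given dose, so the same divisor cannot serve both.

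These are the outputs meant to show whether an ethnic difference in exposure is a weight difference. If the groups differ in weight and exposure does not rise with weight, the adjusted summaries enlarge the weight effect or create a false one. If the lighter group truly has lower exposure, they can hide it. Table 2.1.5 could also show one group with both higher adjusted exposure and higher adjusted clearance, which has no coherent reading.

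**Working it through.** **Inputs.** From the documents: fixed 100 µg on Day 1; CL/F = Dose/AUC0-inf; the division by weight (WT) in SAP 12.3.3; BMI matching within ±15%. Assumed, because the documents give none: group weights, heights, and the dependence of clearance on weight. There is no figure in the plan to reproduce.

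**1. Direction.** (CL/F)/WT = Dose/(AUC0-inf × WT). The exposure that mirrors it is AUC0-inf × WT / Dose, exactly 1/[(CL/F)/WT]. With the SAP's two definitions,

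(AUC0-inf/WT) × (CL/F)/WT = Dose/WT²,

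which varies between subjects, whereas AUC0-inf × CL/F = Dose does not. Example in arbitrary units: Dose 100 and CL/F 100 for both a 55 kg and a 70 kg subject. AUC is 1.0 in each. AUC/WT is 0.01818 vs 0.01429, and CL/F per kg is 1.818 vs 1.429. The lighter subject appears higher on both. The identity is exact for AUC0-inf only; AUClast and Cmax follow the same dose-per-kg reasoning without it.

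**2. Effect on the group ratio.** Let R be the unadjusted Japanese/Caucasian geometric mean ratio at 100 µg and r the Japanese/Caucasian geometric mean weight ratio among the subjects contributing the parameter. Then

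- parameter/WT gives R/r;
- parameter × WT / Dose gives R × r.

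Both are exact for geometric means and need no pharmacokinetic assumption. At r = 1 neither moves the ratio.

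**3. Does matching hold r at 1?** For a pair, Caucasian/Japanese weight = BMI ratio × (height ratio)². The BMI tolerance alone allows 0.85 to 1.15 at equal height. At equal BMI, Caucasian subjects 2.5%, 5% or 8% taller (assumed) give 1.025² = 1.051, 1.05² = 1.103 and 1.08² = 1.166. So matching does not hold r at 1, though the tolerance limits are single-pair extremes, not group means.

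**4. No ethnic effect.** Take CL proportional to WT^b, so R = r^(−b), R/r = r^(−(b+1)) and R × r = r^(1−b).

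| Weights (assumed) | b | Unadjusted R | SAP: AUC/WT | AUC × WT / Dose |
|---|---|---|---|---|
| 65 vs 70 kg | 0 | 1.000 | 1.077 | 0.929 |
| | 0.5 | 1.038 | 1.118 | 0.964 |
| | 0.75 | 1.057 | 1.138 | 0.982 |
| | 1 | 1.077 | 1.160 | 1.000 |
| 60 vs 70 kg | 0 | 1.000 | 1.167 | 0.857 |
| | 0.5 | 1.080 | 1.260 | 0.926 |
| | 0.75 | 1.123 | 1.310 | 0.962 |
| | 1 | 1.167 | 1.361 | 1.000 |

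At equal BMI these weights imply height ratios of √(70/65) = 1.038 and √(70/60) = 1.080. The second is an upper illustration. Cmax follows the same algebra with its own unknown exponent.

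**5. Hiding.** At 60 vs 70 kg, R = 0.857 gives AUC/WT = 0.857/0.857 = 1.000. The per-kg clearance ratio is then 1/(0.857 × 0.857) = 1.361.

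**6. When each form helps (log scale, no ethnic effect).**

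- AUC/WT is further from 1 than no adjustment for every b > −0.5. It is exact only at b = −1, that is, exposure proportional to weight.
- AUC × WT / Dose beats AUC/WT for b > 0 (tie at b = 0) and beats no adjustment for b > 0.5.
- If exposure rises with weight, the order reverses: at b = −0.5 and 60 vs 70 kg, R = 0.926, AUC/WT = 1.080 and AUC × WT / Dose = 0.794.

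**The case against.** No comparative estimate depends on these parameters. The Welch ratios and forest plots use values not adjusted for weight, and SAP 2.6 says "the statistical analyses are for exploratory rather than confirmatory purposes". Unadjusted values appear in the same box-plot figure, weight is summarised by ethnic group and listed by subject (SAP 7), and CL/F per kg is tabulated. In the hiding example the 0.857 would still appear in the Welch output, so only someone reading the adjusted panel alone is misled. All of this stands and limits the harm.

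The replacement is also not neutral. It shifts the ratio by the same factor in the other direction. At 60 vs 70 kg with b = 0 it turns 1.000 into 0.857, and it would show a true, weight-independent ratio of 1.167 as 1.000. This stands too. The case for it rests on the dose-per-kg convention and on consistency with the SAP's own per-kg clearance, not on any exponent in the documents.

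Finally, AUC0-inf × WT / Dose only restates CL/F per kg, so the weight-divided exposures could simply be dropped. For AUC0-inf the redundancy is real. It does not extend to AUClast or Cmax, and Figure 2.1.11 does not plot CL/F or Vdz/F per kg: its weight-adjusted panels show only the three affected parameters.

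**Conclusion.** The concern holds. The inconsistency between weight-adjusted AUC0-inf and CL/F per kg is certain, since it follows from the SAP's definitions. AUClast and Cmax share the misdirection by the same reasoning.

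The size is conditional. The group ratio is multiplied by the Caucasian/Japanese geometric mean weight ratio, which the documents do not give. The ranges in the table rest on assumed weights and on an exponent between 0 and 1, and there is no distortion of the group ratio if geometric mean weights are equal. The result is exact for geometric means, not for the medians and quartiles of a box plot. For AUC0-inf it refers to subjects for whom that parameter can be calculated.

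The primary 100 µg comparison and its 90% interval are untouched. The point still deserves correction, because the affected outputs are the ones addressing the weight question raised in Protocol 3.2, and Cmax has no clearance-type counterpart to reveal the problem.

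**What to change.** In SAP 12.3.3, define weight-adjusted AUClast, AUC0-inf and Cmax as parameter × body weight / Dose, and keep division by weight for CL/F and Vdz/F only. Dividing by Dose is needed because Table 2.1.5 also covers 25 and 50 µg; otherwise dose-proportional values would differ 1:2:4 across 25, 50 and 100 µg. State the proportionality assumption, keep the unadjusted values alongside as planned, and say which weight is used, since it is measured at screening and on Day -1.

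Optionally, add a supportive 100 µg comparison of log exposure with log weight as a covariate, which does not fix the exponent in advance. A lesser alternative is to drop the weight-divided exposures and rely on CL/F and Vdz/F per kg, which leaves Cmax without a weight-adjusted form.

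The cost is three formulas and minor reprogramming of one table, one listing and one figure, with no new data. The downside is over-correction relative to no adjustment if exposure depends only weakly on weight (b below 0.5), and a result further off than the present formula if exposure rises with weight (b below 0).

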12.3.4 Statistical Analysis of Pharmacokinetic Parameters

12.3.4.1 Descriptive Statistic Analysis of PK Parameters

All PK parameters (original, baseline-adjusted, body weight-adjusted, and dose-normalized-baseline-adjusted) of rhPTH(1-84) will be listed and summarized with descriptive statistics (number, arithmetic mean, SD, coefficient of variation [CV%], median, minimum, maximum, geometric mean, %CV of geometric mean, and 95% confidence interval of the geometric means) by ethnic group and dose..

The geometric mean and individual values of dose-normalized baseline-adjusted PK parameters vs dose in Japanese subjects will also be presented in plots.

Box-Whisker plots for selected PK parameters for 100 μ g dose level will be generated with both ethnic groups side by side. These PK parameters are C_{max} and AUC_{last} based on original concentrations, and baseline-adjusted C_{max} , AUC_{last} , AUC_{0-inf} , and body weight adjusted baseline-adjusted C_{max} , AUC_{last} , and AUC_{0-inf} .

